Statistical Analysis Plan (SAP)

The PACE Study

Post Affordable Care Act: Evaluation of Community Health Centers

[figure not shown]
AHRQ R01HS024270
NCT 02657499

January 1, 2019

**A partnership between:
Oregon Health & Science University
OCHIN, Inc.**

B.4.4 Statistical Analysis.

We will use validated OCHIN data and Medicaid claims data to assess the impact of Medicaid expansion on healthcare access, receipt of healthcare services, and Medicaid expenditures. We will summarize baseline measures using descriptive statistics and data visualization methods (e.g., histograms, scatter plots) across clinic and state groups. Our primary criteria for studying Medicaid expansion will be estimating differences in outcomes described in Box 7 (above) between individuals and clinics in (a) expansion versus non-expansion states over the 12-months pre- and at least 24-months post-Medicaid expansion time periods (Aim 1), (b) in expansion states only (Aim 2), and (c) in Oregon (Aim 3). As seen in Box 8, the ACA-Medicaid expansion took effect January 1, 2014. Eight states in the OCHIN EHR data adopted Medicaid expansion at the start of 2014. Their pre-period is 12-months prior to 2014 (i.e., 2013) and their post-period extends from the time of expansion to the end of the project. (For most expansion states, the post-period will be 2014 through 2017; however, we are aware that some non-expansion states may expand during the study period, so we will take this into account in our analyses). Our primary methodological approach will utilize difference-in-differences (DID) methodology. The DID approach has been frequently used by health services researchers to account for potential secular effects and changing policies that would affect both expansion and non-expansion states over time, while adjusting for potential confounders.¹⁶⁷⁻¹⁷²

The general analysis for **Aim 1** is represented by the following equation:

$$Y_{ijkt} = f(\alpha + \beta M_k + \gamma \tau_t + \theta M_k \tau_t + \delta Z_{ijkt})$$

where Y_{ijkt} represents individual i 's performance on an outcome measure of interest (i.e., insurance coverage,) nested within the j th clinic in state k at time t ; M_k represents a dummy variable taking a value of 1 in expansion-state and zero otherwise; and τ_t is a dummy variable taking a value of 1 if the observation took place after Medicaid expansion and 0 otherwise, Z_{ijkt} is a matrix of potential individual, clinic, or state confounders and f represents a general function that captures our intent to model a variety of outcome types through generalized linear mixed models (GLMMs).¹⁷³ The coefficient α is an overall intercept representing average baseline performance for all individuals; β represents the incremental baseline performance differential between clinics in expansion and non-expansion states and γ represents the change in performance pre- and post-expansion for all clinics. The coefficient of interest θ captures the relative performance improvement in outcomes for the patients in expansion versus non-expansion states over time. In this model, non-expansion states will serve as the reference. This equation is very general but can be adapted to include dummy variables for each time period or a continuous variable to capture linear time trends.

To address Aims 2 and 3, we can use a modification of the equation presented above. For **Aim 2**, the indicator M_k will be replaced with two indicator variables to represent the three insurance groups (newly insured, already insured, and uninsured) of interest. For **Aim 3**, the indicator M_k will be substituted by a binary variable denoting newly insured versus already insured. This equation can also be adapted to have the clinic serve as the unit of measurement instead of the individual. There are multiple options for estimating our DID approach. Our preferred method is to implement state random effects in clinic-level analyses and both clinic and state random effects in patient-level analyses to control for correlation of observations nested in clusters (e.g., individuals nested in clinics which are nested in states). Clinics and

states will be treated as random effects because Medicaid expansion may vary across clinics and states. However, we recognize that the assumption for random effects may not be met and we will also assess the robustness of our assumptions by running models that treat clinics and states as fixed effects. We will formally test the validity of the random effects using the standard Hausman test¹⁷⁴ and assess overall qualitative differences that may arise between the random and fixed effects models.

We will use GLMM,¹⁷³ which offer flexible regression modeling to accommodate different sources of correlations (serial, intra-clinic, and intra-state), categorical and continuous covariates, and fixed and time-dependent covariates. These methods offer a wide range of parametric distributions to model the dependent variables, including logistic regression (binary data), beta regression (percent data), Poisson regression (count data), and Gaussian regression (normally distributed data). For example, to assess a change in services utilized, a logistic mixed-effects regression model can analyze services received in pre- and post-expansion periods as a function of whether a patient belongs to CHC in a state that did or did not expand Medicaid and other possible confounders (e.g., predisposing factors; need for services). The distribution of the outcomes of interest will be examined before selecting an analysis model; specific models will be refined through an iterative process, guided by the hypotheses, conceptual model, and preliminary analyses. If we find significant patient panel or clinic differences in states that did or did not expand Medicaid (Aim 1) or in patients who are newly insured, already insured, and uninsured (Aim 2), we will use propensity score weighting methods to reduce the observed bias, help minimize external threats to the validity of the results and adjust for imbalances between intervention and comparison clinics.¹⁷⁴ [name] (PhD biostatistician) will lead these decisions and determine the need for additional models.

Econometric analyses for Aim 3. Using DID methods, we will calculate the average pre-post difference in total Medicaid expenditures attributable to the subpopulation of newly insured patients in Oregon OCHIN CHCs, subtracted by the average difference among the already insured patients. We will assess changes in spending immediately after Medicaid expansion in Oregon clinics as well as comparing subsequent years post-expansion. Specifically, we will first assess the initial increase in Medicaid expenditure after the expansion (post t_1). In this case, because newly insured were uninsured at the pre-period, thus incurring no cost to Medicaid, their cost will be equal to \$0. Next, we will assess the change between post at t_1 (i.e., 2014) versus post at t_2 (i.e., 2015) versus post at t_3 (i.e., 2016) to evaluate whether the initial cost-increase is reduced overtime and by how much. Changes in spending after Medicaid expansion among newly insured vs. spending changes in already insured will 'net out' any secular changes not related to Medicaid expansion. Any remaining significant differences in outcome – DID – are attributed to Medicaid expansion. These findings will help to assess whether Medicaid expansion can help reduce costs, and if so, whether the reduction comes from lowering the spending associated with unnecessary or inefficient use of services external to CHCs. We note that CHCs do not have incentives to act as gatekeepers to this care. Therefore, reductions in spending for these external services would most likely reflect improvements in care delivery within CHCs. Analytically, the DID estimate is represented by the marginal effect on the interaction between a dummy variable indicating that the observations occur in the post-Medicaid expansion period and a dummy variable indicating newly insured individuals. We will also include patient-level variables to account for predisposing factors and need for services, as identified by the Aday and Andersen model. A variety of factors must be addressed in our DID estimation: *Accounting for clinic-level effects.* Our study will focus on the 'treatment-effect' of the Oregon Medicaid expansion: How does expanding Medicaid affect healthcare spending? Since this is our main focus, our approach is to use clinic-level fixed effects to net out any time-invariant differences in clinic-level outcomes. However, recognizing the potential interest in clinic-level effects, in secondary analyses we will test hierarchical (mixed) models to more

specifically model (i) clinic-level variation and (ii) patient-level variation. *Modeling health care expenditures.* As in many analyses of a patient's healthcare expenditures, in any given year, many patients will have no visits. Thus, our dependent variable will have a cluster of observations at zero. We will use a well-validated approach for modeling this phenomenon: the 2-part model.¹⁶¹ Part 1 will use a logistic regression to estimate the probability of any expenditure. Part 2 will focus on individuals with non-zero expenditures. We will use recent literature to guide the appropriate estimation approach, taking into account the potentially skewed distribution of the dependent variable.^{162,163}

For **Aim 1**, the primary dependent variables are insurance coverage, utilization of services, and receipt of preventive services in the pre- and post-expansion periods, in expansions versus non-expansion states. To assess service utilization, we will ask questions such as: Has the overall number of CHC services (e.g., visits, immunizations, referrals) increased? To assess preventive services, we will use clinical quality metrics for process (e.g., blood pressure screening rates in the clinic). The primary independent variable is whether a CHC is in a state that expanded Medicaid or not. For **Aim 2**, the primary dependent variables are utilization of services and receipt of preventive services among cohorts of individual patients in expansion states. To assess service utilization, we will ask questions such as: Has the number of primary care visits, per patient, increased? To assess preventive services, we will use clinical quality metrics for process (e.g., breast cancer screening rates among patient cohorts). The primary independent variable is whether a patient is newly insured, already insured, or uninsured. For **Aim 3**, the primary dependent variables are utilization of services in CHCs and external to CHCs and Medicaid expenditures in Oregon. To assess service utilization, we will ask questions such as: What is the rate of hospitalizations in newly versus already insured patients? To assess Medicaid expenditures, we will ask: Are there differences in Medicaid expenditures between newly insured versus already insured patients? Do expenditures plateau over time for newly insured patients? The primary independent variable is whether an Oregon patient is newly insured or already insured. Other covariates for patient- and clinic-level analyses in the three aims include predisposing factors and need for services as described in Box 6, above.

Methods to account for non-users in the post-period. The available data do not indicate whether patients without clinic contact in the post-period are true non-users, or drop-outs (*i.e.*, left the clinic permanently to seek care elsewhere), potentially leading to underestimated utilization rates. A dropout rate that is similar across groups will not impact the comparison between clinics in expansion versus non-expansion states or between patients with different coverage status, but differential dropout poses a threat to the generalizability of the findings. As a sensitivity analysis, we will use pre-expansion data to model the probability that a patient has a visit in year t based on demographic information and the number of visits to the clinic in year $t-1$ and $t-2$. Parameters from this model will be used to attach a weight to all patients across all years. This method provides a measure of the contribution of each patient on utilization measures and avoids bias that may arise from defining patient attribution according to utilization patterns that occur because of the Medicaid expansion.

Standard errors adjustments. Depending on the distribution of the outcomes of interest, standard errors may be difficult to estimate using standard regression variance output. Thus, we plan to implement bootstrapping to obtain reliable standard errors when appropriate. Additionally, as a sensitivity analysis, we plan to bootstrap all analytic models simultaneously to allow estimating covariances among parameter estimators across models.

Power calculations. For **Aim 1**, our total sample size includes 761,840 patients distributed over

442 clinics in 16 states. We estimated power accounting for the clustering of patients within clinics and clinics within states. This sample size will provide 90% power in patient-level analyses to detect a minimum of 1.9% difference in changes in binary outcomes before and after Medicaid expansion, when intra-cluster correlation (ICC) is set to 0.10.¹⁷⁵ For example, this corresponds to a scenario where the pre- and post-expansion change of percent of covered visits is +6.0% in the Medicaid expansion group and +4.1% in the non-Medicaid expansion group assuming an ICC=0.10. As most studies show an ICC<0.001,¹⁷⁵ the proposed study will have sufficient power to detect differences of health policy importance. We will also have 90% power to detect a 2.7% difference in changes of binary outcomes, assuming an even more conservative ICC=0.20. For clinic-level analyses, this sample size will provide 90% to detect a minimum of 2.3% difference in binary outcomes before and after Medicaid expansion with an ICC=0.10. For continuous outcomes, the study sample will provide 90% to detect a 0.26 difference in change in mean before and after Medicaid expansion (ICC=0.10). This corresponds to a scenario where the pre- and post-expansion change is +0.30 for clinics in expansion state and +0.04 for clinics in non-expansion state. For **Aim 2**, with a sample size of 447,488 patients, the comparisons of newly insured compared to already insured and uninsured will have 90% power to detect a difference of 3.35%. For example, this corresponds to a scenario where newly insured patients increased covered visits +4.55% (pre vs. post) and only +1.2% increase in covered visits for already insured from pre to post. For **Aim 3** (sample size of 187,684), a comparison of newly insured versus already insured will have 90% power to detect difference in changes in binary outcomes before and after Medicaid expansion of 2.8% assuming an ICC=0.10. Estimates of parameters for all of these power calculations were obtained from a preliminary pull of OCHIN EHR data. **We note that power calculations estimate the minimum numbers needed to detect changes. In reality, the impact of Medicaid expansion could be much greater than these minimums.** Although these calculations are simplistic and do not account for all differences among clinics or propensity score matching, we expect our actual analyses will have a similar or greater power as regression adjustment results in increased precision for certain outcomes and thus increased statistical power.¹⁷⁶

B.4.5 Dissemination. This study is extremely timely as many states are still deliberating on whether to expand their Medicaid programs, and other states are eager to learn about the impact of their expansions. Our study findings will need to be rapidly disseminated to inform these policy discussions. We have expertise in working with community partners, healthcare practitioners in OCHIN, and state and national policymakers to rapidly and widely disseminate policy-relevant research findings.¹⁷⁷ In addition, our approach to use OCHIN EHR data to study natural policy experiments has broad relevance to the study of national and local healthcare reform efforts. Thus, we will also endeavor to disseminate methods for using and further validating this dataset as we have done successfully with previous studies.^{33,36,56,58,59} Finally, as the results of this project unfold rapidly, we recognize the importance of sharing real-time lessons and implementation experiences to a broad national audience. We will leverage our previously launched and supported blog, funded by the Robert Wood Johnson Foundation, to provide information and opportunities for blog readers to dialogue about the implications of health policy reforms¹⁷⁸ (see more specific information in the attachment describing our Data Sharing Plan).

B.4.6 Study considerations. (1) We will use EHR data or Oregon EHR-Medicaid data; EHR data alone have inherent limitations, but as noted above, outperform claims data and/or self-reported data. EHR data sources are not developed for research purposes; however, we have conducted multiple data validation studies, built EHR research datasets, and successfully conducted policy-relevant research in the past.^{22,33,34,53,59,61} The combination of EHR and claims

data addresses some of the limitations reported when these individual data sources have been used alone.²⁹ **(2)** We anticipate missing data, either from services documented in inaccessible parts of the EHR (likely random) or from patients who went outside the OCHIN network to receive services (perhaps not random). Our analyses can accommodate missing data resulting from attrition of patients. We will explicitly model missingness by including variables that are related to missingness in the analysis as covariates.¹⁷⁹ If non-trivial levels of missing data are observed, we will use a method such as multiple imputation to include these patients in analyses.¹⁸⁰ We will conduct a sensitivity analysis comparing parameter values for models using completers only, all patients without multiple imputation, and all patients with multiple imputation, to understand any biases introduced by differential attrition and/or missing not at random.¹⁸¹ **(3)** As with any 'real-world' study, unobserved changes might occur over time, making it difficult to isolate the effect of the ACA. Patients from expansion and non-expansion states may prove to be very different on average. If so, we plan to perform a propensity score matching of patients to identify the most closely matched patients in expansion and non-expansion states. This propensity score matching along with the use of both clinic- and patient-level analyses, and the use of a DID approach will help minimize these biases.

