Exclusion Criteria	Our study population included adults aged 19-64 insured by Oregon Medicaid continuously from January 2014 through December 2015. We excluded patients without coverage on 1/1/2014 and those with coverage gaps during the study period. We excluded patients with dual Medicaid and Medicare eligibility and whose 2014-2015 eligibility did not depend on FPL (e.g. pregnant women). Of 622,513 adults aged 19-64 with any 2014 Medicaid enrollment, 230,602 (37%) remained in our sample.
Independent Variables	Insurance group, time, and their interaction terms, mean monthly expenditures.
Dependent Variables	standardized expenditures for inpatient care, prescription drugs, and total outpatient care in addition to subdivisions of outpatient: outpatient claims were classified as either emergency department, dental, mental and behavioral health, primary care evaluation, management, and procedures, specialist evaluation, management, and procedures, and primary care/specialist imaging or tests based on a hierarchical system involving procedure code, provider type, provider specialty, place of service, and associated costs.
Covariates	The patient's age, sex, racial and ethnic background, rural setting, and comorbidity level as assessed by the enhanced Charlson comorbidity index score.
Analysis Plan	Retrospective cohort study using inverse-propensity weights to adjust for differences between groups. We summarized enrollee

	utilization outcomes as mean monthly expenditures, running a separate (two-part) hurdle model for each type.
Data Set Name	NPAT, INPATIENT_Q42015, OUTPAT, OUTPATIENT_2015Q4, RX , RX_Q42015, SAMPLE, SAMPLE_with_weights FY_2015_FR_AND_CN_Table 5, Nov 2013 Fee Schedule – Excel, January 2014 Behavioral Health Fee Schedule, January 2014 Mental Health Fee Schedule – Excel
Code Location	Box at OHSU

Medicaid Coverage Accuracy in Electronic Health Records

Full Citation	Marino, M., H. Angier, S. Valenzuela, M. Hoopes, M. Killerby, B. E. Blackburn, N. [name], J. [name], B. Hatch, J. P. O' Malley and J. E. DeVoe (2018). Medicaid Coverage Accuracy in Electronic Health Records . Prev Med Reports 11 : 297–304.
Objective	To evaluate the validity of EHR data for monitoring longitudinal Medicaid coverage and assess variation by patient demographics, visit types, and clinic characteristics.

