For projects that are primarily research, you must submit your *IRB* application accompanied by the signed, dated approval. If you have any question about what constitutes research, please contact the Manager of Health Programs Analysis and Measurement Unit.

RESEARCH APPLICATION

Please use this template to fill in your information

Applicant Name: OCHIN, Inc.

Applicant Address: [name]

Applicant Contact Name: [name], DPhil, [contact], [contact]

1. Describe the general purpose of study.

The purpose of the “*Long-term Trends in Health Insurance Coverage and Access to Health Care Services*” study is to understand trends in health insurance coverage and access to health care services over time in a safety net population. This will include investigating health insurance coverage patterns and differences in health insurance coverage reported in OCHIN versus the Oregon Health Plan [(OHP) Oregon’s Medicaid Program]. We will look at health care services patients receive and how health insurance coverage impacts these services. Additionally, we will look at how health insurance patterns and health care services change as state and federal policies are implemented (for example, the Affordable Care Act, or Coordinated Care Organizations) in Oregon as well as the other states with OCHIN clinics. We will also compare the use of electronic health record tools to keep patients insured.

2. Describe the specific details of the request:

a. Detail the purpose of request, state the research or evaluation question(s), hypotheses to be tested:

This study will 1) examine the relationship between health insurance coverage and receipt of health care services, alone and in relation to policy change, 2) track changes in health insurance patterns and health care services, alone and in relation to policy change, 3) assess differences between OCHIN and DMAP data, and 4) evaluate the use of electronic health record tools to keep patients insured.

b. Specify the data elements/information that is requested from DMAP, which enrollment and claims data elements for specific date periods:

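### Aim 3 credits a fall in external spending to better care in CHCs, but its newly-versus-already-insured contrast within CHC patients cannot identify that cause

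*SAP*

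**What the plan says.** The SAP (B.4.4, Econometric analyses for Aim 3) takes the mean pre-to-post change in Medicaid spending "attributable to the subpopulation of newly insured patients in Oregon OCHIN CHCs, subtracted by the average difference among the already insured patients". In the general model of B.4.4, the expansion-state indicator "will be substituted by a binary variable denoting newly insured versus already insured". For clinics, "our approach is to use clinic-level fixed effects to net out any time-invariant differences in clinic-level outcomes"; hierarchical models are secondary.

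The SAP says that setting changes in the newly insured against "spending changes in already insured will 'net out' any secular changes not related to Medicaid expansion". It credits what remains to Medicaid expansion. Medicaid cost in the newly insured is fixed at $0 before expansion, and the years 2014 (t1), 2015 (t2) and 2016 (t3) are then compared to see whether the first rise shrinks.

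The same paragraph says the results should help show whether savings come from less unnecessary use of care outside the CHCs. It gives a premise, "We note that CHCs do not have incentives to act as gatekeepers to this care", and from it concludes that "reductions in spending for these external services would most likely reflect improvements in care delivery within CHCs".

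On the population, the combined document (Study Population and Study Period) links Oregon CHC records to Medicaid claims. Its IRB protocol (section 5d) limits the expenditure analysis to people found in both sources. Hypothesis 3a expects external use to fall in the newly insured and utilization to stay level in the already insured. Hypothesis 3b expects spending in the newly insured to rise and then level off relative to the already insured.

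**The concern.** The SAP moves from an effect of gaining coverage to a statement about why external spending fell. A contrast between two insurance groups who both attend CHCs carries little information on CHC care. An improvement that reaches both groups is subtracted out. A decline that belongs only to the newly insured stays in, whatever its cause. The missing gatekeeping incentive removes one rival explanation and leaves others open, for example unmet need that is worked off in the first years of coverage.

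At stake is the reading of the savings result. A decline peculiar to the newly insured could be presented as evidence of better CHC care, while a real improvement across CHC patients could leave the DID near zero. The SAP's dissemination section (B.4.5) addresses the findings to states still deciding on expansion.

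**Working it through.** The plan states no figure on this point, so there is none to reproduce. The check is algebra, with assumed dollar values for illustration.

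**Inputs from the documents**
- Contrast: newly minus already insured, Oregon OCHIN CHC patients (SAP B.4.4; IRB protocol 5d).
- Medicaid cost of the newly insured before expansion: $0 (SAP B.4.4).
- Comparator outside the CHCs, measure of CHC care delivery in the spending model, mediation analysis: none stated for Aim 3.

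**Step 1: where a reduction can appear.** With a pre-period value of $0, the first change in the newly insured is post − 0, which cannot be negative. A fall in their Medicaid spending can show only across t1, t2 and t3.

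**Step 2: what the DID contains.** Let S be the secular change common to both groups. Let D be the fall caused by better CHC care in the newly insured, and rD the same fall in the already insured. Let U be a fall confined to the newly insured for another reason.
- Newly insured: S − D − U
- Already insured: S − rD
- DID = (S − D − U) − (S − rD) = −D(1 − r) − U

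One estimate cannot separate D, r and U.

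**Step 3: numbers.** Assumed: S = +$50, and a fall of $200 of one kind or the other. The simulation fitted group, period and their interaction with clinic fixed effects (121 clinics of 400 patients, 40 replicates).

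| Scenario | Newly insured change | Already insured change | DID | Simulated DID |
|---|---|---|---|---|
| D = 200, r = 1 | −150 | −150 | 0 | −5.7 |
| D = 200, r = 0.75 | −150 | −100 | −50 | −50.2 |
| D = 200, r = 0.5 | −150 | −50 | −100 | −100.2 |
| D = 200, r = 0.25 | −150 | 0 | −150 | −147.2 |
| D = 200, r = 0 | −150 | +50 | −200 | −203.3 |
| D = 0, U = 200 | −150 | +50 | −200 | −199.0 |

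The −5.7 in the first row has a standard deviation of 16.5 across replicates, so a Monte Carlo error of 16.5/√40 = 2.6. It lies 5.7/2.6 = 2.2 such errors from zero. The argument rests on the algebra; the simulation only illustrates it.

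The last two rows are identical in every analytic column. The change in the newly insured alone is −150 in every row, so it does not discriminate either. The already insured column does show a shared fall (first row), although it cannot say whether that fall is due to CHC care or is secular.

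**Step 4: scale.** Cancellation depends on the model scale. If both groups fall by 20% from assumed baselines of $1,700 (newly) and $2,000 (already insured), the ratio of ratios is 0.8/0.8 = 1.00, but the dollar DID is −0.2 × 1,700 + 0.2 × 2,000 = −340 + 400 = +$60. The SAP plans a two-part model and leaves the method for its second part open.

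**The case against.** The best defense is that the sentence is a hedged aside. The stated question is how expanding Medicaid affects spending, the residual is credited to expansion, and neither Hypothesis 3a nor 3b mentions CHC care delivery. No model term or decision rule uses the sentence. This stands, and it is why the point is minor. It does not rescue the sentence, because the same paragraph offers the source of savings as something the findings will help to settle.

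A second defense is that a CHC-wide fall need not be hidden. Hypothesis 3a predicts no change in utilization among the already insured, so a fall there would contradict it. That is fair for utilization. The SAP does not commit to reporting external spending separately by group.

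A third is that improved care may mean better care for the newly insured in particular. The DID can register that (r below 1), but cannot separate it from U or from coverage itself.

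Several stronger readings are tempting and are not supported:
- A reader might infer that every CHC improvement is lost. Only the part shared equally on the model scale cancels.
- A reader might infer that clinic fixed effects erase the improvement. They remove only time-invariant differences; the cancellation comes from the subtraction.
- A reader might cite "the Affordable Care Act, or Coordinated Care Organizations" as a rival Oregon policy. The phrase gives undated examples in a data request for a study with a different title, and an effect common to both groups would also cancel.
- A reader might infer that a non-CHC comparator stands ready, since the Oregon expenditure analysis states no CHC restriction: "Of 622,513 adults aged 19-64 with any 2014 Medicaid enrollment, 230,602 (37%) remained in our sample". Its listed files are labelled only to 2015, no CHC-versus-non-CHC weights are planned, and enrollees not linked to OCHIN may use other CHCs.

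**Conclusion.** Wrong as written; minor severity. The Aim 3 contrast does not identify CHC care delivery as the cause of a fall in external spending. A negative DID is neither necessary for a CHC-wide improvement (r = 1 gives $0) nor sufficient for one (U = 200 with D = 0 gives −$200). The size in this study is unknown, because the dollar values are assumed and only show the structure.

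The conclusion rests on both groups being Oregon OCHIN CHC patients. That follows from the linkage and inclusion rules; no sentence says that both groups attend the same clinics. If the mix of groups differs across clinics, some of a clinic's improvement could remain in the DID, still without a way to attribute it. A reader might go further and infer that the main Aim 3 DID is invalid. This point does not support that: the estimate for Medicaid expansion is not affected.

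**What to change.** 1. In SAP B.4.4, Econometric analyses for Aim 3, delete the attribution sentence. Alternatively, replace it with a statement that the contrast estimates the difference in change between newly and already insured CHC patients and does not identify CHC care delivery as the cause.
2. Commit to reporting the change from t1 to t3 in external use and external spending separately in each insurance group, alongside the DID. A shared fall then becomes visible, though not attributable.
3. Optional and exploratory only: compare with Oregon Medicaid enrollees not linked to OCHIN CHCs. This needs new weights for CHC versus non-CHC status, 2016 data for t3, and a caveat that unlinked enrollees may use other CHCs.

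Items 1 and 2 cost one edit and one table from quantities that the DID already requires. Item 3 is real extra work on a question that the Aim 3 hypotheses do not ask, and it should not delay the first two.
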